Hypothesis 3b: Prescription-related costs associated with illness treatment plans will be significantly less in children de-labeled as penicillin allergic.

C. BACKGROUND, SIGNIFICANCE, AND RATIONALE

Children often present to the pediatric emergency department with a parent reported allergy to medications. Allergy to an antibiotic in the penicillin family (hereafter termed penicillin) is the most commonly reported medication allergy, reported in 5-20% of patients.¹⁻⁶ Since physicians and advanced practice providers (hereafter termed providers) rely on these patient/parent reported allergies when making treatment decisions, a large group of patients are denied first-line antibiotic therapy due to misunderstood or misdiagnosed penicillin allergy.⁷ As a consequence, patients are prescribed second or third line medications that are more expensive and not the antibiotic of choice for their bacterial infection.^{8,9} An example of the health risks associated with

reported penicillin allergy was highlighted by Macy et al who found that, “A penicillin “allergy” history, although often inaccurate, is not a benign finding at hospital admission. Subjects with a penicillin “allergy” history spend significantly more time in the hospital, are exposed to significantly more antibiotics associated with Clostridium difficile (C. diff) and Vancomycin-Resistant Enterococci (VRE) and are associated with increased hospital use.”⁹ Additionally it has been shown that de-labelling patients reported to have penicillin allergy can lead to decreased prescription costs with very low rates of subsequent adverse reactions.¹⁰ Specific to penicillin allergy, greater than 95% of patients may actually tolerate a penicillin, either because they were never allergic or because they had an earlier allergy that subsequently resolved.¹¹

Our prior work utilized a novel structured penicillin allergy questionnaire in the PED and found that 76% of the children with penicillin allergy reported by families had exclusively low-risk allergy symptoms for true allergy (Table 1).¹² These symptoms were often adverse reactions, inconsistent with true allergy.¹³⁻¹⁵

Table 1: Categorization of Allergy Symptoms

Low Risk Group		High Risk Group	
Non-Allergic Symptoms	Low-Risk Symptoms	High-Risk Symptoms	
Runny nose	Rash	Facial swelling	Seizures
Diarrhea	Itching	Difficulty breathing	Rash*
Headache	Dizziness	Lip swelling	Itching*
Vomiting with med administration	Vomiting	Wheezing	Vomiting**

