Objective

Our primary objective is to demonstrate the feasibility of utilizing a novel penicillin allergy questionnaire in the PED to identify a low-risk group of patients who will complete an oral challenge in the PED to test for an IgE-mediated allergic reaction. This project will begin as a single site feasibility study, however including up to 2 other collaborative sites for enrollment has been favorably discussed. We do not anticipate this to be a single IRB scenario and will submit a timely comprehensive amendment if plans become concrete and the initial data here proves reliable.

Our secondary objective is to examine whether health care outcomes and prescription-related costs are comparable between children who are de-labeled as penicillin allergic after an oral challenge compared to a standard of care group who are not challenged in the PED.

Aim 1: Demonstrate that a low-risk group of children with reported penicillin allergy will complete an oral penicillin challenge during a pediatric emergency department visit.

Design/setting:

This will be a prospective study of children (2-16) presenting to the PED at the Children's Hospital of Wisconsin with a child or parent reported allergy to penicillin.

Population:

[figure not shown]
Inclusion Criteria: Children aged 2-16 with a parent/guardian (hereafter termed parent) reported history of allergy to a penicillin antibiotic in which the reported allergic reaction occurred at least twelve months prior to the current PED visit.

Exclusion Criteria: Children will be excluded:

- If they have a history of severe developmental delay or inability to communicate the effects of an allergic reaction (non-verbal). ED care team discretion can be utilized to determine ability to proceed with study with regards to developmental delay.
- History of a severe allergic reaction to skin tests
- Anaphylaxis in the past six weeks
- Current pregnancy
- Child is currently on a beta blocker medication
- Children who present to the PED with a rash
- Children who present with multiple episodes of vomiting on day of presentation
- Children presenting to the ED for asthma exacerbation
- Patients deemed too acutely ill for participation as deemed by the ED patient care team
- Non-English speaking families
- Wards of the state, in foster care or police custody or detention will be excluded.

Study Procedure (Figure 1):

Figure 1: Study Procedures for Full Protocol

¹Red boxes indicate oral-challenge-only study procedures

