
Design/setting and study population:

This study will include all children from Aim 1 who underwent an oral challenge in the PED after being determined to have low-risk symptoms on the allergy questionnaire.

Study Procedure (Figure 1, Aim 2)

- 1) A follow-up phone call will be made to all families whose child received an oral challenge.
- 2) If a family receives a one-time dose of antibiotic but does not receive a prescription for a penicillin antibiotic then they will be called on day 1 by a research team member who will administer a 5-minute allergy questionnaire that will review any possible symptoms of allergic reaction following the ED visit.
- 3) If a family receives a penicillin antibiotic prescription following the oral challenge, then they will be called on days 1 and 7 by a research team member for a 5-minute allergy questionnaire that will review any possible symptoms of allergic reaction following the ED visit.
- 4) The patient's primary medical provider will also be notified of the oral challenge results for both groups of patients via fax within 7 days of the oral challenge date.

Aim 3: Examine health care outcomes and prescription-related costs associated with illness treatment plans in children who are de-labeled as penicillin allergic after an oral challenge.**Design/setting and study population:**

This study will include children identified as having low-risk symptoms of allergy from Aim 1 who underwent an oral challenge (Group 1), and those who did not undergo an oral challenge in the PED (Group 2).

Study Procedure (Figure 1, Aim 3)

- 1) A follow-up 5-minute phone survey will be completed by research staff to the family. This follow-up will occur after their initial PED visit at 6 and 12 months.
- 2) The follow-up survey will include questions on health care outcomes since the PED visit that include but are not limited to: the number and type of diagnosed infections, number and type of antibiotics given, and allergic reaction history.

E. TOTAL NUMBER OF HUMAN RESEARCH PARTICIPANTS PROPOSED FOR THIS STUDY AT THIS SITE AND GLOBALLY. WHAT ARE THESE NUMBERS BASED ON?

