Descriptive characteristics will also be used to summarize the baseline patient characteristics and follow-up questionnaire responses for months 6 and 12 of the children who underwent the oral challenge in Aim 1. We will then conduct a three-level economic cost savings analysis. First, in order to calculate the potential cost savings if amoxicillin is filled for all penicillin allergic de-labelled patients, the median retail price of each non-penicillin antibiotic filled will be compared to the median retail price of amoxicillin. Second, we will calculate the cost avoidance savings assuming that patients who fill any amoxicillin/penicillin prescriptions would have filled cefdinir in its place. Lastly, we will extrapolate the total cost savings potentially generated by the approximately 6,700 patients per year treated in our PED who report penicillin allergy.

Sample Size Justification/Power Analysis:

We have determined that we need 50 patients to complete the oral challenge for the feasibility study to be complete. We will consent for questionnaire-screening approximately 250 children to achieve that number. This number is based off of our previous study; during that study 50 patients were approached per month for survey participation, 80% (40) agreed to participation, and 25% (10) of patients were found have high-risk symptoms of allergy and thus were found to be ineligible. Assuming that 50% of patients with low-risk symptoms will have either provider/family refusal to oral challenge this will leave approximately 15 patients per month to complete an oral challenge. Of the 50 children who complete the oral challenge, we estimate that 40 patients will receive a one-time oral challenge and 10 patients will receive an oral challenge and be sent home with a prescription. This estimation is based off of our previous study where approximately 20% of children who were eligible and willing to be tested were discharged home with a prescription antibiotic. If we are able to reach our enrollment goal prior to approaching 500 patients, we will end the feasibility study.

P. FINANCIAL RELATIONSHIPS

The study is funded with internal funds from the section of Pediatric Emergency Medicine and a grant from the Children's Research Institute which support the costs of accomplishing the oral challenges and other associated project costs.

Q. ADVERTISEMENTS / FLIERS

N/A

R. BIBLIOGRAPHY (*list pertinent literature references*)

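### Level two of the cost analysis fixes cefdinir as the drug replaced, and no level uses the unchallenged group that the protocol names as cost comparator

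*Combined protocol and SAP*

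**What the plan says.** Section O (Data Analysis) sets out three levels of cost analysis. Level one compares the median retail price of each non-penicillin antibiotic filled with that of amoxicillin, as a potential saving among de-labelled children. For level two it states: "we will calculate the cost avoidance savings assuming that patients who fill any amoxicillin/penicillin prescriptions would have filled cefdinir in its place". Level three scales a saving up to about 6,700 patients a year. Section O gives no source for the choice of cefdinir, no sensitivity analysis and no interval, and it summarises the 6- and 12-month responses of challenged children only.

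Other sections describe a comparison. Hypothesis 3b in section B reads: "Prescription-related costs associated with illness treatment plans will be significantly less in children de-labeled as penicillin allergic". The secondary objective in section D sets prescription-related costs of de-labelled children "compared to a standard of care group who are not challenged in the PED". The Aim 3 population is low-risk children "who underwent an oral challenge (Group 1), and those who did not undergo an oral challenge in the PED (Group 2"). The Aim 3 survey at 6 and 12 months covers, among other things, "the number and type of diagnosed infections, number and type of antibiotics given, and allergic reaction history", and section F has the calls going to families of the groups, in the plural.

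**The concern.** Level two replaces a comparator with a constant. What still-labelled children receive is the quantity that determines whether removing the label saves money. The plan intends to ask Group 2 about it, then fixes it at one drug. Level one already recognises that several non-penicillin antibiotics are filled and prices each of them, so the single-drug assumption sits oddly beside it.

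Two things are at stake. First, a figure that is positive by construction cannot count against Hypothesis 3b, yet it could be read as support for it. Second, no other part of section O makes the Group 1 versus Group 2 cost comparison that the secondary objective calls for, so Hypothesis 3b has no analysis attached to it.

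**Working it through.** **Figures the plan states.** It states no saving and no price, so there is no cost result to reproduce. The nearby counts in section O do reproduce: 50 × 0.20 = 10 challenged children leaving with a prescription, and 50 × 0.80 × 0.75 × 0.50 = 15 challenges per month.

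**Level two as written.** Let n be the number of amoxicillin/penicillin fills and D the cefdinir price minus the amoxicillin price. Then

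S2 = n × D.

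No Group 2 quantity appears. For n of at least 1 and D above 0, S2 is positive. With no fills it is zero. The documents give neither price; sections C and K say only that second- and third-line drugs cost more, so the plan itself expects D above 0.

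**Level two with the comparator mix.** Among Group 2 courses let q be the share that are cefdinir, a the share that are penicillin despite the label, and g = (mean price of the other agents − amoxicillin price)/D. Then

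S = n × D × [q + (1 − q − a) × g].

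All values of q, a and g below are assumptions. I take n = 10 for scale only, so S2 = 10.0 D in every row.

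| q | a | g | Bracket | S | S / S2 |
|---|---|---|---|---|---|
| 0.75 | 0.1 | 0.25 | 0.75 + 0.15 × 0.25 | 7.9 D | 0.79 |
| 0.50 | 0.1 | 0.25 | 0.50 + 0.40 × 0.25 | 6.0 D | 0.60 |
| 0.25 | 0.1 | 0.25 | 0.25 + 0.65 × 0.25 | 4.1 D | 0.41 |
| 0.25 | 0.3 | 0 | 0.25 + 0.45 × 0 | 2.5 D | 0.25 |
| 0 | 0.1 | -0.2 | 0 + 0.90 × (-0.2) | -1.8 D | -0.18 |
| 0.25 | 0.1 | 1.5 | 0.25 + 0.65 × 1.5 | 12.3 D | 1.23 |

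The negative row needs other agents cheaper than amoxicillin, which runs against the protocol's own expectation. The last row needs other agents dearer than cefdinir.

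**The same in prices.** Take amoxicillin = 1 and cefdinir = 3 (assumed), with no penicillin in the mix and cefdinir share s. With other agents at 1.5, S2/S = 2/[2s + 0.5(1 − s)], which is 1.23, 1.6 and 2.29 at s = 0.75, 0.50 and 0.25. With other agents at 5 and s = 0.50, it is 2/[0.5 × 2 + 0.5 × 4] = 0.67, an understatement. The direction depends on whether the real mix costs less or more on average than cefdinir.

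**Does repricing alone test Hypothesis 3b?** No. If amoxicillin is the cheapest agent, g is at least 0, so the bracket, and hence S, cannot be negative. Level two also omits the number of courses per child and the cost of non-penicillin drugs that de-labelled children still receive. Cost per child, Group 1 minus Group 2, includes both and can take either sign.

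**Is the Group 2 mix estimable?** The assumed 50% refusal implies about one unchallenged low-risk child per challenged child: 50 × 0.5/0.5 = 50 for the 50 challenged in section O. The number of Group 2 courses is not given. If the observed cefdinir share were 50%, the exact 95% confidence interval would be 19% to 81% with 10 courses, 27% to 73% with 20, and 36% to 64% with 50. That is imprecise but usable.

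**The case against.** The strongest reply is that level two is openly an assumption. The text says so, and its size does respond to the observed number of penicillin fills. That is enough for it to stand as a scenario. It does not supply the comparison that the secondary objective names.

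A second reply is that Group 2 is a weak basis. It arises largely from provider or family refusal and is not randomised, so its antibiotic mix is confounded. The survey asks parents about antibiotics given, not prescriptions filled. Permission for Aim 3 contact is described only as part of the Oral Challenge consent (section D, Aim 1 study procedure; section N), which Group 2 families may not sign. All of this stands: the Group 2 data are planned rather than assured. It argues for an interval and a stated limitation, and does not justify leaving the named comparator unused.

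A third reply is that Aim 3 is secondary in a feasibility study and touches neither the primary objective nor safety. That is correct and limits the weight of the point.

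**Conclusion.** The point holds as a cheap improvement. Level two is positive by construction, given at least one penicillin fill and cefdinir priced above amoxicillin, and no level of the cost analysis uses Group 2. As written, section O cannot test Hypothesis 3b.

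The size is unknown because the documents give neither prices nor mix; the range of -0.18 to 1.23 times level two only illustrates how far the answer depends on what the plan fixes.

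Three stronger readings are tempting and unsupported:
- A reader might infer that level two must overstate the saving. It need not: it understates if the real mix costs more on average than cefdinir.
- A reader might infer that level two is the figure scaled to 6,700 patients. Section O does not say which level is extrapolated.
- A reader might infer that pricing level two at the Group 2 mix would by itself test Hypothesis 3b. It would not, because the result still cannot be negative when amoxicillin is the cheapest drug.

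**What to change.** 1. For Hypothesis 3b, compare antibiotic cost per child between Group 1 and Group 2 over 12 months, using the planned survey responses and median retail prices, with a 95% confidence interval. Add Group 2 to the 6- and 12-month summaries.
2. Price the level-two counterfactual at the antibiotic mix observed in Group 2, including any penicillin, with an interval. Keep all-cefdinir as a labelled scenario. If Group 2 courses are few, also show scenarios with cheaper and dearer alternatives. The level-one mix should not stand in for Group 2, because those fills come from de-labelled children. The likely number of courses does not support splitting the mix by diagnosis.
3. State which level is extrapolated to the 6,700 patients.

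The cost is SAP wording, a weighted average and a two-group comparison on survey data already planned, plus clarification of how Group 2 families consent to being contacted. The estimate will be imprecise and possibly smaller. It will rest on parent report and be confounded by non-random membership of Group 2; the SAP should state these limits beside the result.

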We have determined that we need 100 low-risk patients to complete the oral challenge at each of the three sites participating including here at Children's Hospital of Wisconsin. We will consent for questionnaire-screening approximately 500 children to achieve that number. This number is based off of our previous study; during that study 50 patients were approached per month for survey participation, 80% (40) agreed to participation, and 25% (10) of patients were found to have high-risk symptoms of allergy and thus were found to be ineligible. If 50% of patients with low-risk symptoms will have either provider/family refusal to oral challenge this will leave approximately 15 patients per month to complete an oral challenge and complete this portion of the study in approximately 7 months.

F. DRUGS OR PROCEDURES

Patient's family or guardian will be asked to answer an allergy symptom questionnaire that will be administered via an iPad. Patient's charts who are between the ages of 2-16 whose family has indicated an interest in allergy oral challenge will be reviewed.

If a child is eligible as defined in the questionnaire for allergy oral challenge and the family completes the challenge, then a gift card in the amount of \$50 will be provided for their time.

If a family completes all the telephone follow-up questionnaires at 6 and 12 months they will be mailed a \$25 gift card at the conclusion of each of the follow-up calls. (total of \$50 in follow-up stipends for full participation over one year.)

The allergy challenge consists of an oral amoxicillin challenge in the PED. A nurse will administer the oral challenge and will also be present during the process all of which will occur in the PED.

A follow up telephone survey monitoring for any adverse side effects/allergic reactions will be completed within 24 hours of the allergy oral challenge. If a patient receives a prescription for a penicillin or any other antibiotic then a follow up call will be made to monitor for any adverse side effects/allergic reactions at 7 days as well. Patients will also receive discharge instructions relevant to the study with phone numbers to call with questions.

A follow-up 5-minute phone survey will be completed by research staff to families of groups after their initial PED visit at 6 and 12 months. PI will review these results monthly or as relevant (notified by the study team) to monitor the long-term outcomes and safety of the protocol.

G. RISK CATEGORY:

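### Sections O and E give this site two different targets for completed oral challenges, 50 and 100, without saying that they are separate stages, so the stop in Section L can mean either

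*Combined protocol and SAP*

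**What the plan says.** **Section O, Sample Size Justification/Power Analysis:** "We have determined that we need 50 patients to complete the oral challenge for the feasibility study to be complete". The paragraph continues: "We will consent for questionnaire-screening approximately 250 children to achieve that number". It expects that "10 patients will receive an oral challenge and be sent home with a prescription", and closes with: "If we are able to reach our enrollment goal prior to approaching 500 patients, we will end the feasibility study".

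**Section E:** "We have determined that we need 100 low-risk patients to complete the oral challenge at each of the three sites participating", with this hospital named as one of them. It continues: "We will consent for questionnaire-screening approximately 500 children to achieve that number". From the same previous study it concludes that "this will leave approximately 15 patients per month to complete an oral challenge and complete this portion of the study in approximately 7 months".

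**Section D, Objective:** "This project will begin as a single site feasibility study, however including up to 2 other collaborative sites for enrollment has been favorably discussed". Further sites would come in by a later amendment if plans firm up.

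**Section C** describes a multi-center study as the long-term goal.

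**Section L** ends the study when the sample size has been accrued. It gives no number and does not refer to another section.

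**Section O, Data Analysis** plans descriptive percentages, with 95% confidence intervals for positive challenges and for delayed reactions.

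**The concern.** Two sections state a required number of completers for the same hospital, from the same recruitment assumptions, and the numbers differ by a factor of two. Neither text is marked as superseded. A planned sequence, 50 first and then more, would remove the conflict, but no sentence sets one out. Section D treats the other sites as a possibility, while Section E counts them as already taking part.

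The target governs how many children at this site are challenged, in research that Section G classes as greater than minimal risk. It is also the only quantity on which Section L's stop depends. If enrolment at this site ended at 50, the feasibility study would be complete under Section O, yet the site would be at half of what Section E says is needed.

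**Working it through.** **Inputs (the same in Sections E and O unless noted)**
- Approached per month: 50
- Agree to the questionnaire: 80%
- High-risk and therefore ineligible: 25%
- Provider or family refusal among the low-risk: 50%
- Discharged with a prescription: 20% (Section O)
- Completer target: 50 (Section O), 100 per site (Section E)
- Duration: about 7 months (Section E only)

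**1. Reproduce the plan's monthly figure.** 50 × 0.80 = 40 consented; 40 × 0.75 = 30 low-risk; 30 × 0.50 = 15 completers per month. This matches both sections. The yield is 15/40 = 37.5% of those consented and 15/50 = 30% of those approached.

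**2. See which target each section's other figures fit.**

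| | Target 50 | Target 100 |
|---|---|---|
| Months at 15 per month | 50/15 = 3.3 | 100/15 = 6.7 |
| Discharged with a prescription, at 20% | 10 | 20 |

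Section E's 7 months fits 100, and Section O's 10 prescriptions fit 50. Each number is built into its own section, so a typing slip in one of them is unlikely.

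**3. See whether Section O's ceiling of 500 approached children identifies the target.** At 30%, 50 completers need 50/0.30 = 167 approached (rounded up), and 100 need 100/0.30 = 334. Both lie below 500, and 500 approached would give about 150 completers. The ceiling singles out neither target.

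**4. Precision under each target.** With no positive challenges among n children, the exact (Clopper-Pearson) two-sided 95% upper limit is 1 − 0.025^(1/n):
- n = 50: 7.1%
- n = 100: 3.6%

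**5. Day-7 group.** Hypothesis 2b asks for day-7 follow-up in at least 90% of children discharged on an antibiotic. That would mean 9 of 10 children, or 18 of 20.

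**6. Section E's consents against its duration.**
- Consented in 7 months at 40 per month: 7 × 40 = 280
- Consents needed for 100 completers: 100/0.375 = 267 (rounded up)
- Months to consent 500: 500/40 = 12.5

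The 7 months agrees with about 267 to 280 consents, not with 500. The figure of 267 assumes that every completer enters by consenting to the study questionnaire. Sections D and N also describe children who had the nursing questionnaire and consent to the challenge only, and these fall outside this calculation.

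**The case against.** The strongest reply is that the plan is staged and the two numbers belong to different things. Section O limits 50 to the feasibility study. Section D says the project starts as a single-site feasibility study. Section E ties 100 to three sites and calls it a portion of the study. Section C looks ahead to a multi-center study. Read together, 50 is the single-site phase and 100 per site is the expansion. This is the likely intention, and it stands as a reading. What it lacks is a sentence that links the numbers to the stages. Section E also applies 100 to this hospital, so it remains open whether this site continues past 50 and whether the first 50 count toward the 100.

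Three stronger readings are tempting and should be resisted.

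- **That the study has no numerical end, or that stopping at 50 would be premature.** The documents do not support this for the feasibility study. In Section O's closing sentence the enrollment goal most naturally means 50, the only completer target in that paragraph. Section L's silence on the number would be harmless if the other sections agreed.
- **That the analysis is compromised.** It is not. The confidence interval will be computed on the children actually challenged, and no power, margin or interval width depends on the target. The 7.1% and 3.6% show what each target could deliver if no challenge is positive. Neither is a criterion of the plan.
- **That the counts of 250 and 500 are sample-size errors.** Both imply a 20% yield (50/250 = 100/500), against 37.5% from the stated rates. They are given as approximate and err on the generous side, so no shortfall follows. Nor does Section E's 500 consented conflict with Section O's 500 approached, because these are different quantities. Only the mismatch between 500 consents and 7 months within Section E remains.

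**Conclusion.** The inconsistency is real: the current text gives this site a target of 50 in one section and 100 in another, and Section L's stop can refer to either. The size is two-fold in the number of children challenged. This corresponds to a zero-event upper limit of 7.1% or 3.6%, a day-7 group of about 10 or 20 at the plan's 20% prescription share before any loss to follow-up, and 3.3 or 6.7 months of accrual at 15 per month.

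This is an internal inconsistency in the sample size, wrong as written. The monthly recruitment arithmetic is correct in both sections. It should be fixed, but it does not threaten the validity of a descriptive analysis whose targets come from neither power nor precision. A staged plan is the probable explanation, and the conclusion does not depend on rejecting it. The mismatch between Section E's 500 consents and its 7 months is a minor addition, and the 267 used there holds only if all completers enter through study questionnaire consent.

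**What to change.** - **Sections E and O:** state one completer target per site and in total. If stages are intended, name both, give each its own number, and say whether the first 50 at this site count toward the 100.
- **Sections D and E:** describe the status of the other sites in the same way, either conditional on an amendment or already taking part.
- **Section L:** cite the number, or the section that holds it.
- **Section E:** make the consents and the duration agree. Either use a count near 267 to 280, or label 500 as a ceiling that allows for a lower yield. Note that children who enter through the nursing questionnaire are not counted in it.

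The cost is a wording change in these sections; if staging was intended, one linking sentence settles the main point. No added enrolment is needed. The one small drawback is that keeping 50 means showing a less favourable precision.
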